- previous history or current diagnosis of neoplasms and/or anti-neoplastic therapies within 5 years from randomization
- history of diabetic ketoacidosis
- current therapies with steroids and/or anti-psychotic medications
- any concomitant conditions which can preclude participation in the study

Female participants in fertile age have to use contraceptives during the study. Moreover, women who meet inclusion criteria will be screened for pregnancy before the completion of the enrollment.

Randomization

Randomization using a computer generated random-number sequence.

Allocation

Concealed in sealed study folders that will be held in a central, secured location until after informed consent will be obtained.

Interventions

LIRA GROUP: participants assigned to LIRA group will start on 0.6 mg once daily liraglutide subcutaneous injection at approximately the same time of the day. The dose will be titrated up on a weekly schedule by 0.6 mg increase to a target dose of 1.8 mg or the maximum tolerated. In accordance with standards of medical care, cardiovascular risk factors will be managed as follows:

systolic blood pressure below 130 mmHg and diastolic blood pressure below 80 mmHg obtained, if needed, with ACE inhibitors or angiotensin receptor blockers, LDL-cholesterol below 70 mg/dL, aspirin therapy at the dosage of 100 mg daily or alternatively clopidogrel 75 mg daily in case of documented aspirin allergy.

CONTROL GROUP: individuals assigned to control group will be given, if needed, tailored therapeutic prescriptions to manage blood glucose levels and cardiovascular risk factors, according to the standards of medical care. The established treatment goals for cardiovascular risk factors control will be: systolic blood pressure below 130 mmHg and diastolic blood pressure below 80 mmHg obtained, if needed, with ACE inhibitors or angiotensin receptor blockers, LDL-cholesterol below 70 mg/dL, aspirin therapy at the dosage of 100 mg daily or alternatively clopidogrel 75 mg daily in case of documented aspirin allergy.

Recruitment and time schedule

Recruitment will last 18 months. Participants will be followed up for 24 weeks (6 months).

Time schedule	Visit 1 (Screening)	Visit 2 (Randomization)	Visit 3 (3 months follow- up)	Visit 4 (End of the study)
	Week -1	Week 0	Week 12	Week 24
Informed consent	x			
Eligibility evaluation	x			
Pregnancy screening test [†]	x			
Start of the intervention		x		

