Anamnesis and clinical assessment	x			
Physical examination: weight, BMI, WC		x	x	x
Blood pressure evaluation		x	x	x
Glycemic profile evaluation: fasting glucose, HbA _{1c}	x	x	x	x
Lipid profile evaluation: total cholesterol, LDL-chol, HDL-chol and triglycerides		x	x	x
Renal function evaluation: creatinine, azotemia, eGFR	x	x	x	x
Inflammation markers: CRP, fibrinogen, TNF- α and IL-6		x		x
Angiogenesis markers: EPCs and VEGF		x		x
Sexual hormones evaluation: testosterone or estradiol, LH, FSH, SHBG*		x		x
Albuminuria		x		x

ABI and 6-minute walking test		x		x
TcPO ₂	x	x	x	x
IIEF-5 questionnaire*		x		x
FSFI questionnaire†				
Adverse events evaluation		x	x	x

*In males; †In females.

ABI, Ankle Brachial Index; BMI, Body Mass Index; CRP, C-reactive protein; EPC, Endothelial Progenitor Cell; eGFR, estimated Glomerular Filtration Rate; FSFI, Female Sexual Function Index; FSH, Follicle-stimulating hormone; IL-6, Interleukin 6; IIEF-5, International Index of Erectile Function 5; LH, Luteinizing hormone; SHBG, Sex hormone-binding globulin; TcPO₂, Transcutaneous Oxygen Pressure; TNF- α , Tumor Necrosis Factor α ; VEGF, Vascular Endothelial Growth Factor; WC, Waist circumference.

Study withdrawal

Subjects may withdraw from the research at any time for:

- voluntary retirement;
- occurrence of adverse event which requires the end of the study;
- poor adherence to trial intervention and/or follow-up;
- modification of inclusion/exclusion criteria from baseline;
- novel treatment with medications interfering with the endpoints evaluation;
- pregnancy.

Investigators may interrupt the research in case of:

- occurrence of adverse events (nausea, vomit, abdominal pain, fever, rush and/or eosinophilia);
- renal function worsening (eGFR <15 mL/min/1.73m²);
- dialysis or renal transplantation;
- chetoacidosis (confirmed by laboratory tests);
- occurrence of acute or chronic pancreatitis;
- medullary carcinoma diagnosis after randomization;
- any adverse event or relevant clinical event, considered as an interference for the research;
- any allergic reactions;
- recruitment of the individual in other study interfering with the research.

Primary outcomes

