Descriptive statistics will be used for demographic and baseline clinical characteristics of all participants in the study. Continuous variables will be described as either mean and standard deviation (SD) or medians and interquartile range (IQR) according to sample distribution, and count data will be reported as numbers and percentages. Comparisons of baseline data between groups will be performed by Student's t test or Mann-Whitney Rank Sum test, depending on the normality of sample distribution. Comparison among frequencies was made with the χ^2 test.

To evaluate the change of variables over time Δ values will be calculated as value at the last observation minus value at the start. The paired t test and Wilcoxon signed rank test within each patients' group will be used to assess changes in the studied variables from baseline to the last observation. Two-sample t-test will be used to compare differences between interventions. The χ^2 test will be used for comparing proportions of participants in the 2 groups who reached the primary endpoint after the intervention. Relative Risk (RR) and 95% confidence interval (CI) will be calculated to demonstrate the relationship between the intervention and the achievement of the primary endpoint. Data were also analyzed by analysis of variance for repeated measures with a post-hoc comparisons made with the Scheffé's test. P value < 0.05 will be considered statistically significant. All analyses will be conducted using SPSS version 19.0 (SPSS Inc, Chicago, Ill).

Safety and Adverse Events

Adverse event (AEs) - Any unexpected event occurred in a patient included in a clinical trial after the administration of a pharmacological product. This event is not necessarily related to pharmacological treatment. Therefore, an AE, may be any unpleasant and unwanted clinical sign (for example, an abnormal laboratory finding), symptom, or disease, which is transiently associated with the use of a drug. According to the guidelines of the Common Terminology Criteria for Adverse Events (<https://www.fda.gov/downloads/Guidances/UCM174090.pdf>), AEs will be divided in different grades.

- Grade 1 (mild): lack of symptoms or mild symptoms, with no indication to specific intervention; clinical or diagnostic observation is required.
- Grade 2 (moderate): moderate symptoms requiring local or non-invasive intervention; it may determine a limitation of daily activities.

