- Grade 3 (severe or clinically significant, but not immediately life-threatening): requiring hospitalization. It may determine disability and heavily limit daily activities.
- Grade 4 (life-threatening event): indication to urgent intervention.
- Grade 5: death related to AE.

Adverse drug reaction (ADR) - An ADR is defined as a noxious and unintended response to drug administration. It occurs determining pathological changes with doses which are normally used in

humans for prophylaxis, diagnosis, or therapy of a disease. The relationship between the drug administration and the adverse event is reasonably possible and, in any case, cannot be excluded.

Serious Adverse Event (SAE) – A SAE is defined as any adverse clinical event that is fatal or life-threatening, which requires hospitalization and leads to a significant disability. It also includes congenital anomalies/birth defects, or any serious medical event that investigator would report.

Hospitalization will be considered as SAE if:

- duration of hospitalization lasts more than 12 hours;
- hospitalization was not previously planned;
- hospitalization is not connected to an AE.

Disability is defined as the significant loss of any ability useful for carrying out normal vital functions.

Unexpected Adverse Reaction or Suspected Unexpected Serious Adverse Reaction (SUSAR) – A SUSAR is a severe and unexpected reaction which is also considered unpredictable, according to drug information (for example, medication data sheet).

Overview of Adverse Event Evaluation

- Type, frequency, severity and severity/intensity of all AEs
- Number of patients discontinuing treatment due to the occurrence of any AE
- Clinically significant changes in ECG, vital signs and laboratory tests

If any AE/SAE occurs, investigator will have the responsibility to report the suspected adverse drug reaction to the Service of Pharmacovigilance, in accordance with current legislation. Moreover, serious adverse events must be notified to pharmacovigilance manager within 24 hours of the awareness. Furthermore, SUSARs must be notified to the Authorities and Ethical Committee.

Pregnancy

Pregnancy is an exclusion criteria for the study, since GLP-1RAs have no indications in pregnancy. If pregnancy occurs in patients taking liraglutide:

- 1) treatment with liraglutide will be immediately stopped;
- 2) pharmacovigilance manager will receive notification (within 24 hours);
- 3) women will be monitored until the end of the pregnancy.

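### The adverse event definition is limited to unexpected events after giving a drug, which conflicts with the protocol's own use of the term and gives the control arm no clear start for counting

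*Protocol*

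**What the plan says.** The only definition of an adverse event stands in the protocol under Safety and Adverse Events. It has three parts.

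- It opens with "Any unexpected event occurred in a patient included in a clinical trial after the administration of a pharmacological product".
- It adds "This event is not necessarily related to pharmacological treatment".
- It concludes that an AE may be "any unpleasant and unwanted clinical sign (for example, an abnormal laboratory finding), symptom, or disease", with the qualifier "which is transiently associated with the use of a drug".

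Four other places bear on it.

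- Study withdrawal lists, among the reasons for which investigators may interrupt the research, "occurrence of adverse events (nausea, vomit, abdominal pain, fever, rush and/or eosinophilia" (closing bracket omitted here).
- The SUSAR paragraph reads "A SUSAR is a severe and unexpected reaction which is also considered unpredictable, according to drug information".
- The overview of adverse event evaluation promises type, frequency and severity for all AEs, and the number of patients who stop treatment because of any AE.
- The time schedule marks AE evaluation at weeks 0, 12 and 24, without distinction by arm.

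On treatment, "participants assigned to LIRA group will start on 0.6 mg once daily liraglutide subcutaneous injection". The control group receives no liraglutide and no placebo, only prescriptions as needed for glucose and cardiovascular risk factors.

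**The concern.** The opening sentence sets two conditions that do not belong in a general AE definition: the event must be unexpected, and it must follow administration of a product. The first condition is the one the protocol uses elsewhere to single out SUSARs. The second has an obvious anchor in the liraglutide arm and none in the control arm.

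What is at stake is consistent recording. The safety output is a tabulation of AEs by type, frequency and severity. If investigators apply the definition differently, or if its starting point differs between arms, part of any difference in AE frequency may come from recording. Without a placebo, the two arms also have no common first dose that would set the same clock for both.

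**Working it through.** The protocol states no figure that depends on this definition, so there is nothing to reproduce. The check is a comparison of passages.

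**1. Expectedness against the withdrawal list.** The definition asks for an unexpected event. Study withdrawal names nausea, vomiting, abdominal pain and other symptoms beforehand and calls them adverse events. A symptom foreseen in the protocol sits badly with a definition restricted to the unforeseen. The conflict is one of wording: the protocol does not say that these symptoms are expected according to the drug information, and the point does not need that.

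**2. Expectedness against the summary.** The overview covers all AEs and has no limit by expectedness. Under the literal definition, *all AEs* would mean all unexpected ones. Nothing in the overview suggests that this is intended.

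**3. Expectedness against the SUSAR test.** For a SUSAR, *unexpected* is judged against drug information and helps decide what must be notified to the authorities and the ethics committee. If every AE is unexpected by definition, the word no longer separates a SUSAR from other serious reactions. The definition of an adverse drug reaction adds to the tangle. It rests on a relationship between drug administration and the adverse event, so a foreseeable drug reaction would, literally, not be an AE.

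**4. Do the later sentences repair it?** The second sentence removes the need for a causal link but leaves expectedness untouched. The third widens the kind of event and carries no expectedness condition. It is introduced as a consequence of what precedes it, however, and it brings a limit of its own, the transient association with a drug. Read literally, that limit could exclude a lasting event. The reader has to decide which sentence governs.

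**5. Start of counting, by arm.**

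| | Liraglutide arm | Control arm |
|---|---|---|
| Study product | Liraglutide, started at week 0 | None; no placebo |
| Other drugs | Metformin and/or insulin at entry; risk-factor drugs | Metformin and/or insulin at entry; risk-factor drugs |
| AE evaluation | Weeks 0, 12, 24 | Weeks 0, 12, 24 |
| What *after administration* refers to | Most naturally the first liraglutide dose | Long-standing metformin or insulin, a new prescription, or nothing definite |

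The schedule fixes when participants are asked. It does not fix the date from which an event counts.

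**6. Scale.** The planned sample is at least 50 participants in a 1:1 ratio, so 50 / 2 = 25 per arm. One participant classified differently moves the proportion with an AE in an arm by 1 / 25 = 4 percentage points. This shows how sensitive small arms are; it does not estimate how many events would be missed.

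**The case against.** The strongest reply is that the opening sentence should not be read alone. The same paragraph drops the need for causality and extends to any unwanted sign, symptom or disease. The withdrawal list tells investigators that nausea, vomiting and abdominal pain count. The overview speaks of all AEs. Read as a whole, the protocol evidently intends to record such events. Safety is also not among the primary or secondary outcomes, and no analysis or sample size rests on the definition.

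Much of this stands, and it rules out three stronger readings.

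- A reader might infer that foreseeable drug effects will be left out. That follows only if the first sentence is taken in isolation; the rest of the paragraph, the withdrawal list and the overview point the other way.
- A reader might infer that control-arm events can be left out altogether. The text refers to a pharmacological product and to a drug, not to the study drug. Every participant enters on metformin and/or insulin, both arms have aspirin or clopidogrel among their risk-factor measures, and AE evaluation is scheduled for everyone.
- A reader might try to put a number on the missed events. The protocol gives no event rates, and any assumed rate would yield a count only by presupposing the disputed literal reading.

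The reply does not remove the internal conflict. If the intent has to be recovered from other sections, the definition does not say what the sponsor means. Nor does the reply supply a common start of counting for the two arms.

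**Conclusion.** The point holds as a minor defect in a stated rule. The definition, read literally, disagrees with the withdrawal section, with the planned summary of all AEs and with the separate role of expectedness in the SUSAR definition. It also leaves the control arm without a clear start for counting, so recording could differ between arms in a trial without placebo.

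The conclusion rests on the wording alone and needs no assumption about event rates. Whether recording would in fact differ depends on how investigators read the paragraph, which the protocol does not settle. The size of any effect on AE counts cannot be derived from the document. The primary analysis and the sample size are not touched.

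**What to change.** Replace the opening sentence so that an AE is any untoward medical occurrence in a participant of either arm, from randomization to the end of the study, whether or not it is expected and whether or not it is related to a drug. Delete the phrase "which is transiently associated with the use of a drug". Use expectedness only in classifying SUSARs, where the protocol already ties it to drug information.

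This brings the definition into line with the withdrawal section and the overview, and gives both arms the same counting window. It costs a small rewording of one paragraph and slightly more events to record. The visit schedule, the outcomes and the sample size need no change.

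### The SAE and SUSAR definitions are internally inconsistent, so the 24-hour notice and the SUSAR notice for some serious events rest on the investigator's reading

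*Protocol*

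**What the plan says.** All the relevant text is in the protocol, under Safety and Adverse Events.

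- **SAE, core sentence.** An SAE is an adverse clinical event that is "fatal or life-threatening, which requires hospitalization and leads to a significant disability".
- **SAE, further routes.** The next sentence adds alternatives: "It also includes congenital anomalies/birth defects, or any serious medical event that investigator would report".
- **Hospitalisation list.** Under "Hospitalization will be considered as SAE if" there are three bullets: a stay of more than 12 hours, an admission not planned beforehand, and "hospitalization is not connected to an AE". Nothing says whether all three must hold or any one is enough.
- **SUSAR.** The heading expands the abbreviation with the word *Serious*. The defining sentence reads: "A SUSAR is a severe and unexpected reaction which is also considered unpredictable, according to drug information".
- **What the definitions trigger.** Under Overview of Adverse Event Evaluation, "serious adverse events must be notified to pharmacovigilance manager within 24 hours of the awareness". SUSARs go to the authorities and the ethics committee, with no time limit stated. Separately, for any AE or SAE the investigator must report the suspected reaction to the pharmacovigilance service under current law, again with no time limit of the protocol's own.

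**The concern.** Only the first two terms of the core SAE sentence are joined by *or*. Hospitalisation and disability are attached to them as further conditions. On that wording a death at home is outside the sentence, and so is an admission with full recovery or a disabling event treated as an outpatient. The hospitalisation list shows that this cannot be what was meant, so the section contradicts itself.

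The SUSAR sentence has a related fault. Severity is how intense an event is, and seriousness is what it leads to. The protocol uses *severe* as the label of Grade 3, so the SUSAR sentence defines a seriousness category by an intensity word and never points to the SAE definition.

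SAE status triggers the 24-hour notice, and SUSAR status triggers the notice to the authorities and ethics committee. If the triggers can be read in more than one way, two investigators can handle the same event differently.

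**Working it through.** The protocol gives no figure here to reproduce. The check reads the definitions as logical conditions.

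**Step 1: the core SAE sentence.** Let F = fatal or life-threatening, H = requires hospitalisation, D = leads to significant disability. The non-empty combinations number 2³ − 1 = 7. If each criterion were sufficient alone, all 7 would be SAEs. The literal sentence needs F and H and D.

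| Combination | Literal core sentence | Hospitalisation list, bullets cumulative | Hospitalisation list, bullets alternative |
|---|---|---|---|
| F only | no | no | no |
| D only | no | no | no |
| F + D | no | no | no |
| H only | no | no | yes, if unplanned or over 12 hours |
| F + H | no | no | yes, if unplanned or over 12 hours |
| H + D | no | no | yes, if unplanned or over 12 hours |
| F + H + D | yes | not needed | not needed |

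The core sentence covers 1 of 7 and leaves 6. These are logical combinations, not expected numbers of events.

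**Step 2: the hospitalisation list.** An adverse event that requires admission produces, by construction, an admission connected to an AE. If the three bullets are cumulative, the third bullet shuts out every such admission, so the list rescues 0 of the 6. It would then admit only admissions unconnected to an AE, although the section defines an SAE as an adverse event and describes Grade 3 events as requiring hospitalisation. If the bullets are alternatives, the list rescues 3 of the 6, subject to the length or planning condition. Pancreatitis, named under Study withdrawal, is an example: an unplanned admission with full recovery fails the core sentence, fails the cumulative list and passes the alternative list.

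**Step 3: the catch-all.** What remains (6 combinations if the bullets are cumulative, at least 3 if they are alternatives) can still be an SAE as a serious medical event that the investigator would report. That route uses *serious* to define serious and depends on what the investigator chooses to report. It can bring these events back in, but only by discretion.

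**Step 4: the SUSAR sentence.** The grading scale calls Grade 3 severe or clinically significant and links it to hospitalisation. Grade 4 is life-threatening and Grade 5 is death.

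- If *severe* means Grade 3 or above, most reactions that involve admission, threat to life or death are covered.
- What is left is a reaction that is serious under the SAE text but graded below 3 or not readily graded, such as a medically important event.

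**Step 5: what an event loses if it is not recognised.** The general duty to report to the pharmacovigilance service covers any AE or SAE. An event missed as an SAE therefore loses the protocol's 24-hour limit. A reaction missed as a SUSAR loses the notice to the authorities and ethics committee.

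**The case against.** The strongest reply is that this is loose drafting that nobody would apply literally. The section goes on to elaborate hospitalisation and disability separately, which makes sense only if each is a criterion in its own right. The catch-all is a true alternative, the SUSAR heading supplies the missing word, and the general reporting duty stands behind everything. Much of this is right, and it limits the size of the point. It does not remove the point, because the rescue routes are discretionary or ambiguous and the one most often needed, the hospitalisation list, contains a bullet that may exclude the events in question.

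A reader might infer more than the document supports:

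- **That many serious events escape notification.** This is not shown. The catch-all, the hospitalisation list and the general duty can bring many back, and *severe* as Grade 3 or above covers most serious reactions.
- **That these are the protocol's only time-limited safety actions.** They are not. A pregnancy on liraglutide has its own 24-hour notice, and the SUSAR notice has no stated limit.
- **That a birth defect could not be a SUSAR.** This is a weak example. Grade 3 also says clinically significant, and pregnancies on liraglutide are notified and followed separately.
- **That comparisons of SAE counts by arm are compromised.** Such counts are not a listed output in this document.
- **That the overview's "Type, frequency, severity and severity/intensity of all AEs" is a further defect.** The repeated word is an editorial slip, with no shown effect on notification.

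**Conclusion.** The point holds as an internal inconsistency in stated safety rules. The core SAE sentence is wrong as written and contradicts the lines after it. The SUSAR sentence disagrees with its own heading and is not tied to the SAE definition.

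The consequence is bounded. The 24-hour notice for deaths without admission, AE-related admissions and disabling events depends on discretion or on how a list is read. The SUSAR notice is uncertain for serious unexpected reactions graded below *severe*. Reporting as a whole is not lost, and the TcPO₂ outcomes are not touched.

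This rests on two assumptions: that *severe* in the SUSAR sentence carries the meaning of the protocol's own grading scale, and that the list's missing connective leaves both readings open. No number of affected events can be derived from the document.

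**What to change.** 1. Rewrite the core sentence so that each criterion suffices: an adverse event that is fatal, or is life-threatening, or requires hospitalisation, or leads to significant disability, or is a congenital anomaly or birth defect, or is judged medically serious by the investigator.
2. Define a SUSAR as a suspected reaction that is both serious, meaning that it meets the SAE definition, and unexpected.
3. Reconcile the hospitalisation list with the new sentence. State whether its bullets are cumulative or alternative, and resolve the third bullet against the requirement that an SAE is an adverse event. Without this step the rewritten hospitalisation criterion would still collide with the list.

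The protocol's closing note dates the trial's conduct to February 2021 to December 2022. The sponsor should therefore also state which reading was applied and check that deaths, admissions and disabling events were classified consistently under it.

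The cost is a few wording changes, that check, and possibly a few more expedited notifications under the clearer text.

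### The rule for counting a hospitalisation as an SAE has its adverse-event condition inverted, so it conflicts with the protocol's own SAE definition

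*Protocol*

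**What the plan says.** All the relevant text is in the protocol under Safety and Adverse Events.

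- **General SAE definition:** an SAE is "any adverse clinical event that is fatal or life-threatening, which requires hospitalization and leads to a significant disability". The definition also takes in birth defects and "any serious medical event that investigator would report".
- **Hospitalisation list:** this opens with "Hospitalization will be considered as SAE if" and gives three items: a stay of more than 12 hours, an admission not planned beforehand, and "hospitalization is not connected to an AE". It does not say whether the items are joint or alternative.
- **AE definition:** an AE is "Any unexpected event occurred in a patient included in a clinical trial after the administration of a pharmacological product", and the text adds that it need not be related to the drug. Adverse drug reactions are defined separately.
- **AE grading:** Grade 3 is described as an event needing admission.
- **Consequences of classification (Overview of Adverse Event Evaluation):** SAEs go to the pharmacovigilance manager within 24 hours of becoming known. The investigator must also "report the suspected adverse drug reaction to the Service of Pharmacovigilance", and SUSARs go to the authorities and the ethics committee. The evaluation covers "Type, frequency, severity and severity/intensity of all AEs".

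The closing statement after the references says the trial ran from February 2021 to December 2022.

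**The concern.** The lead-in makes this an inclusion list. The first two items point towards SAE status and the third points away from it. An SAE is by definition an adverse clinical event, so a condition requiring that no AE be involved cannot sit in the same rule without contradicting that definition. No other part of the protocol explains or corrects the item.

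This is an operative rule. SAE status starts the 24-hour notification and decides which events are counted as SAEs. Someone applying the list literally and someone applying the general definition can reach different answers for the same AE-related admission.

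**Working it through.** No figure in the protocol bears on this point, so the check is a logical one. Four types of admission are put through the list, as written and with the third item reversed. 'Yes' means that the list makes the admission an SAE.

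| Admission | As written, all items needed | As written, any item enough | Reversed, all items needed | Reversed, any item enough |
|---|---|---|---|---|
| A. Unplanned, over 12 hours, caused by an AE | No | Yes (items 1, 2) | Yes | Yes |
| B. Unplanned, over 12 hours, no AE | Yes | Yes (items 1, 2, 3) | No | Yes (items 1, 2) |
| C. Planned, 12 hours or less, no AE | No | Yes (item 3 alone) | No | No |
| D. Planned, 12 hours or less, connected to an AE | No | No | No | Yes (item 3) |

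1. **Joint reading, as written.** A fails and B passes. The AE-caused admission is left out and the one with no adverse event is let in, which reverses the definition.
2. **Alternative reading, as written.** C becomes an SAE on the third item alone, although no adverse clinical event is present.
3. **Reading 'AE' as 'drug reaction'.** This does not rescue the item. The AE definition says that drug causality is not required, and drug reactions have their own definition.
4. **Reading the list as a misplaced exclusion list.** This also fails, because the first two items would then exclude long, unplanned admissions.
5. **Grade 3 wording.** The grading expects AEs that lead to admission, so type A is a case the protocol itself foresees.
6. **After reversal.** B and D still differ between the joint and alternative readings. Correcting the third item is necessary, but the sponsor must also say how the items combine.
7. **Routes outside the list.** The lead-in says 'if', not 'only if'. An admission that fails the list may still be an SAE under the general definition or under the clause on events the investigator would report.

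**The case against.** The strongest reply is that this is a drafting slip with little practical effect. Two of the three items and the Grade 3 wording show what was meant. The list is not exclusive, the trial is single-centre so sites cannot diverge, and nothing shows that anyone applied the third item literally. AEs are evaluated whether or not they are serious, and suspected reactions and SUSARs have their own reporting routes.

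Most of this stands, and it limits the consequence. It does not remove the contradiction: the sentence is complete and legible, and no reading tested above makes it agree with the definition.

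A reader might infer more than the documents support, in four ways.

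- **That AE-related admissions can never be SAEs.** The word 'if' leaves the other routes open. The 'and' joining hospitalisation and disability in the general definition should not be used to close them. Read that strictly, even a death without admission and disability might fall outside, which is not a plausible intent. The loose 'and' is a wording defect to tidy.
- **That the joint rule would hardly ever be met.** The protocol does not say how often an unplanned admission has an AE behind it.
- **That control participants fall outside the AE definition because they receive treatment only if needed.** Every participant enters on metformin and/or insulin, and the same risk-factor management is set for both arms, so controls also receive pharmacological products.
- **That the SAE proportions shift by a particular amount.** The protocol gives no expected number of admissions, and its sample size is a minimum. Any such figure would rest on invented counts.

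**Conclusion.** The point holds as a contradiction within the protocol's safety section. The third hospitalisation item is inverted relative to the SAE definition and the Grade 3 wording, whether the items are joint or alternative. SAE classification of admissions, and the 24-hour notification that follows from it, is inconsistent but not impossible.

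The size of the effect cannot be determined: the number of affected admissions is unknown and may be zero. Efficacy and sample size are unaffected, and the text gives no ground for saying that adverse-event data are lost. Confidence is high that the wording is wrong; the documents do not show whether any event was misclassified because of it. The correction should be made, because the rule is operative and the repair is cheap.

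**What to change.** 1. Correct the third item so that the hospitalisation is connected to an AE, which brings the list into line with the SAE definition.
2. Separate the criteria in the general SAE definition with 'or'.
3. Have the sponsor state whether the listed items are joint or alternative, and that the list does not narrow the general definition. Whether duration and planning are necessary conditions is for the sponsor to say, because the documents do not establish it.
4. Since the trial has been conducted, check recorded admissions against the corrected rule and report by arm any that change SAE status. New wording alone does not settle past classifications, and it cannot alter notifications already made or missed.

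The cost is two wording corrections and one clarifying statement in a single section, plus a check of the recorded admissions in a single-centre trial. No added visits, procedures or participants are needed.
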